5.6 Duration of Therapy

Treatment may continue for up to 4 cycles of chemotherapy (CE) as described in Section [5.1](#). In the investigational arm (Arm A), nivolumab in combination with chemotherapy (CE) will be given for up to 4 cycles, followed by maintenance nivolumab for up to a total of 2 years (or 50 doses) of treatment with nivolumab as described in Section [5.1](#). Treatment may continue until one of the following criteria applies:

Patients will receive protocol therapy unless:

- Extraordinary Medical Circumstances: If at any time the constraints of this protocol are detrimental to the patient's health, protocol treatment should be discontinued. In this event submit forms according to the instructions in the EA5161 Forms Packet.
- Patient withdraws consent.
- Patient experiences unacceptable toxicity.
- Non-protocol therapies are administered.
- Disease progression as defined in Section [6](#).

5.7 Duration of Follow-up

For this protocol, all patients, including those who discontinue protocol therapy early, will be followed for response until progression, even if non-protocol therapy is initiated, and for survival for 5 years from the date of registration.

6. Measurement of Effect

Rev. Add4

6.1 Antitumor Effect – Solid Tumors

For the purposes of this study, patients should be re-evaluated for response every 6 weeks. All patients will be evaluated for response every 6 weeks for the first 6 months on study, every 8 weeks until 1 year on study, and then every 12 weeks after 1 year on study.

Response and progression will be evaluated in this study using the international criteria proposed by the revised Response Evaluation Criteria in Solid Tumors (RECIST) guideline (version 1.1) [Eur J Ca 45:228-247, 2009]. Changes in the largest diameter (unidimensional measurement) of the tumor lesions and the shortest diameter in the case of malignant lymph nodes are used in RECIST.

The following general principles must be followed:

1. To assess objective response, it is necessary to estimate the overall tumor burden at baseline to which subsequent measurements will be compared. All baseline evaluations should be performed as closely as possible to the beginning of treatment and never more than four weeks before registration.
2. Measurable disease is defined by the presence of at least one measurable lesion.
3. All measurements should be recorded in metric notation by use of a ruler or calipers.
4. The same method of assessment and the same technique must be used to characterize each identified lesion at baseline and during follow-up.

6.1.1 Definitions

Evaluable for Objective Response

Only those patients who have measurable disease present at baseline, have received at least one cycle of therapy, and have had their disease re-evaluated will be considered evaluable for response. These patients will have their response classified according to the definitions stated below.

NOTE: Patients who exhibit objective disease progression prior to the end of cycle 1 will also be considered evaluable.

Evaluable Non-Target Disease Response

Patients who have lesions present at baseline that are evaluable but do not meet the definitions of measurable disease, have received at least one cycle of therapy, and have had their disease re-evaluated will be considered evaluable for non-target lesion assessment. The response assessment is based on the presence, absence, or unequivocal progression of the lesions.

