3.1 Eligibility Criteria

_____ 3.1.1 Age \geq 18 years

_____ 3.1.2 Patients must have histologically or cytologically confirmed extensive stage small cell lung cancer and must be a candidate for systemic therapy

NOTE: The extensive disease SCLC classification for this protocol includes all patients with disease sites not defined as limited stage. Limited stage disease category includes patients with disease restricted to one hemithorax with regional lymph node metastases, including hilar, ipsilateral and contralateral mediastinal, and/or ipsilateral supraclavicular nodes. Extensive disease patients are defined as those patients with extrathoracic metastatic disease, malignant pleural effusion, bilateral or contralateral supraclavicular adenopathy. Patients with locally recurrent SCLC who are not eligible for curative intent chemoradiation are eligible.

Rev. Add1

Rev. Add4

_____ 3.1.3 Patients must have measurable disease based on RECIST 1.1 (see Section [6.1.2](#))

_____ 3.1.4 ECOG performance status 0 or 1 (see [Appendix V](#))

Rev. Add1
Rev. Add4

_____ 3.1.5 Patients must have acceptable organ and marrow function as defined below (these must be obtained \leq 7 days prior to protocol registration)

_____ Absolute neutrophil count \geq 1,500/mm³
ANC: _____ Date of Test: _____

_____ Platelets \geq 100,000/mm³
Platelet: _____ Date of Test: _____

_____ Leukocytes \geq 3000/mm³
Leukocytes: _____ Date of Test: _____

_____ Hemoglobin \geq 9 g/dL
Hemoglobin: _____ Date of Test: _____

_____ Total bilirubin \leq 1.5 X institutional upper limit of normal (ULN) (except subjects with Gilbert Syndrome, who must have total bilirubin $<$ 3 mg/dL)
Bilirubin: _____ Date of Test: _____

_____ AST (SGOT) and ALT (SGPT) \leq 3 X institutional upper limit of normal (ULN) (\leq 5 X ULN if LFT elevations due to known liver metastases)
ALT: _____ Institutional ULN: _____
Date of Test: _____
AST: _____ Institutional ULN: _____
Date of Test: _____

_____ Serum creatinine \leq 1.5 x ULN or calculated creatinine clearance $>$ 50 mL/min (using the Cockcroft-Gault formula)
Serum creatinine _____ Date of Test: _____
or
Creatinine clearance: _____ Date of Test: _____

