11. For Arm B patients on observation, symptom-directed history and physical examinations including vital signs, weight and performance status should be performed every 6 weeks (+/- 7 days) for the first 6 months on study, then every 8 weeks (+/- 7 days) until 1 year on study; and every 12 weeks (+/- 7 days) after 1 year on study, alongside the radiologic evaluations. Labs (CBC w/diff, serum chemistries) are done as clinically indicated. CT scans will be done until disease progression
12. Follow-up after patient discontinues protocol treatment (Arm A) or the end of observation (Arm B): every 3 months for patients < 2 years from registration, every 6 months if patient is 2-3 years from registration, and yearly until 5 years from registration. Patients in the observation phase on Arm B may be seen more frequently per schedule of CT scans as per footnote 9. All patients, including those who discontinue protocol therapy early, will be followed for response until progression, even if non-protocol therapy is initiated, and for survival for 5 years from the date of registration. For all patients during follow-up, symptom-directed history and physical examinations including vital signs, weight and performance status should be performed until progression. Follow-up for survival after progression may occur via phone calls.

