9.3 Statistical Analysis Plan

The primary and some secondary analyses will include all eligible and treated patients. Exception to this include: analysis of toxicity data, which will include all patients who received study drug regardless of eligibility, and analyses of response, which will include eligible and treated patients with measurable disease. Time-to-event data, such as PFS and OS, will be estimated using the Kaplan-Meier method, and Cox proportional hazards models will be used to estimate the treatment hazard ratios. The primary comparison of PFS will use a logrank test stratified on the randomization stratification factors with a one-sided type I error rate of 10%. Other comparisons of groups will be made using the log rank test and Cox modeling. Categorical data, such as response rates (CR+PR) and toxicity, will be compared using Fisher's exact tests with a one-sided type I error rate of 10%; multivariable logistic regression modeling will be used to adjust for the effect of any covariates that are associated with these categorical outcomes. Continuous outcomes will be analyzed using Wilcoxon rank sum test, and multivariable linear regression models may be used to adjust for multiple associations with outcome.

Modeling procedures will implement backward selection; variables significant at the 0.10 level in the univariate setting will be chosen for inclusion in an initial full model, and at each step the least significant variable will be removed from the model. Only those covariates with $p < 0.05$ will remain in any final models, unless there are factors identified by the study team as crucial to model interpretation.

Point estimates of all endpoints will be accompanied by the corresponding 95% confidence intervals; however, 80% confidence intervals will also be provided for

the primary endpoint (PFS) hazard ratio. In the event that there are missing data, no imputation of the missing data will be conducted. We will assume that data are missing at random and will conduct all analyses as originally planned because we do not anticipate an excess of missing data.

Subset analyses are planned for all stratification factors and all known prognostic factors, such as performance status, age, sites of metastases, gender, etc. Subset analyses of all variables, including correlatives, are considered to be exploratory in nature.

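### Does the evaluability rule in section 6.1.1 take treated patients out of the response-rate denominator set in section 9.3?

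*Combined protocol and SAP*

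**What the plan says.** Section 9.3 (Statistical Analysis Plan) lists exceptions to its general analysis set. One is "analyses of response, which will include eligible and treated patients with measurable disease". It requires no minimum exposure and no post-baseline scan. Section 3.1.3 states "Patients must have measurable disease based on RECIST 1.1", so in practice this is the same set as for the primary analysis, planned in section 9.4 at 67 per arm.

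Section 6.1.1 (Definitions) is narrower. It treats as evaluable for response "Only those patients who have measurable disease present at baseline, have received at least one cycle of therapy, and have had their disease re-evaluated", and says that these are the patients whose response is classified. One note widens it: "Patients who exhibit objective disease progression prior to the end of cycle 1 will also be considered evaluable".

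On missing data, section 9.3 says that "no imputation of the missing data will be conducted" and "We will assume that data are missing at random". The second sentence goes on to commit to running every analysis as first planned, because little missing data is expected.

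Section 5.7 says that "all patients, including those who discontinue protocol therapy early, will be followed for response until progression", and footnote 12 of section 7.1 repeats it. Section 9.3 compares CR+PR between arms by Fisher's exact test at a one-sided 10% level.

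**The concern.** Two sections describe the patients in a response analysis and do not match. Two kinds of patient belong to the 9.3 set but fail 6.1.1:

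- **(a)** treated patients with no post-baseline scan, for example those who die, deteriorate or withdraw before the first scan at about week 6 without documented objective progression;
- **(b)** patients who stop before completing one cycle without early objective progression. Sections 5.7 and 7.1 keep them under response follow-up, so one of them could later be scanned, respond, and still not be evaluable.

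The best-overall-response table in section 6.1.4.4 has no row for an unassessed patient, and no sentence calls such a patient a non-responder. An analyst who regarded that scoring as imputation might cite 9.3's missing-data wording for leaving the patient out.

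Both exclusions would depend on what happened after randomisation. Dropping group (a) raises the response rate; dropping group (b) can move it either way. If losses differed by arm, the Fisher comparison would be distorted.

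**Working it through.** **1. The plan's own figure.** No power or sample size is given for response. The stated calculation in section 9.4 is for PFS: 113 events, hazard ratio 5/8 = 0.625, one-sided 0.10. By Schoenfeld's formula, z = (√113 / 2) × |ln 0.625| − 1.2816 = 5.315 × 0.4700 − 1.2816 = 1.216, giving power of 88.8% against the stated 88%. It does not depend on how response is scored. It supplies only the 67 per arm used below.

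**2. The texts side by side.**

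| | Section 9.3 | Section 6.1.1 |
|---|---|---|
| Purpose | Sets analysis populations | Defines measurement terms |
| Requires | Eligible, treated, measurable disease | Measurable disease, one cycle, re-evaluation (or early objective progression) |
| Names a denominator | Yes | No |
| Claims to override the other | No | No |

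The two can be followed together: 9.3 supplies the denominator, and the numerator counts recorded CR and PR. A patient with neither adds nothing to the numerator, and no value has to be imputed. The missing-data wording does not mention removing anyone, and its closing commitment to the planned analyses favours keeping the 9.3 set.

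**3. Effect on the rate if 6.1.1 were the denominator.** The documents give no unscanned share, so the counts are assumptions. Start from 40 responders of 67 = 59.7%, inside the 50-70% quoted for platinum-etoposide in section 1.1.

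- Group (a), 3 unscanned removed: 40/64 = 62.5%, up 2.8 points.
- Group (a), 7 or 10 removed: 40/60 = 66.7%; 40/57 = 70.2%.
- Group (b), 2 removed, neither a responder: 40/65 = 61.5%.
- Group (b), 2 removed, both responders: 38/65 = 58.5%.

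**4. Effect on the test.** Let the true response probability p be equal in both arms over all 67. Remove *a* unscanned non-responders from nivolumab and *b* from control. The response probability among those left is p × 67/(67 − a) or p × 67/(67 − b). Full enumeration of the one-sided 0.10 Fisher test for p = 50, 60 and 70% gives the chance of falsely declaring nivolumab better:

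| Losses (nivolumab v control) | False-positive rate, range over p |
|---|---|
| Equal: 0v0, 3v3, 5v5 | 6.6 to 7.7% |
| Nivolumab +1: 1v0, 4v3, 6v5 | 8.6 to 9.7% |
| Nivolumab +2: 2v0, 5v3, 7v5 | 9.6 to 12.3% |
| Nivolumab +3: 3v0, 6v3, 8v5 | 12.0 to 15.9% |
| Control +3: 0v3, 2v5 | 2.8 to 4.8% |

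The level holds with equal losses or one extra loss on nivolumab. It can be passed at two extra and is passed throughout at three (3/67 = 4.5%). An imbalance the other way makes the test conservative.

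**5. Is an imbalance expected?** Both arms receive the same chemotherapy for cycles 1 to 4 (section 5.1) and share one scan schedule (section 7.1, footnote 9). No passage gives a reason for more unscanned patients on nivolumab.

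**The case for a change.** The strongest argument for acting is that the rule should be fixed before losses by arm are known, and that a sentence costs almost nothing. The word *only* in 6.1.1 is emphatic, the classification it describes is confined to evaluable patients, and the response comparison has a stated test level. A denominator choice can also decide a result. With an assumed 44 v 38 responders, full denominators give 65.7% v 56.7% and one-sided p = 0.188. Dropping 7 v 3 unscanned patients gives 44/60 = 73.3% v 38/64 = 59.4% and p = 0.073.

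What stands is that the scoring convention is unwritten, and that unequal exclusions could matter. The illustration, though, needs both a departure from the population 9.3 sets and an assumed imbalance of four patients. Dropping 3 v 3 gives p = 0.179, and reversing the imbalance to 3 v 7 gives p = 0.327.

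Group (b) adds little. Section 5.1 gives all cycle 1 drugs on days 1 to 3. If those doses count as a cycle, which 6.1.1 does not define, the group is limited to patients who stop within days. To be lost as responders they must also be scanned later and respond before any non-protocol therapy.

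**Conclusion.** The concern does not call for a change. Followed as written, section 9.3 gives a sound response rate and a sound test: all eligible and treated patients with measurable disease in the denominator, documented CR or PR in the numerator. The missing statement that an unassessed patient counts as a non-responder is a detail analysts fill sensibly, and the no-imputation wording does not point the other way.

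Under the less natural reading, the reported rate would rise by about 3 points for an assumed 3 unscanned of 67, and by more if more were unscanned (10.5 points for 10). The Fisher test would stay within 10% unless nivolumab lost at least two more patients than control.

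This rests on 9.3 governing the analysis set, on the two arms having similar early losses, and on assumed counts, since the documents give none. Only a secondary endpoint, listed under estimation in section 9.1, is involved. PFS, OS and the 113-event calculation are unaffected.

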6.1.2 Disease Parameters

Measurable Disease

Measurable lesions are defined as those that can be accurately measured in at least one dimension (longest diameter to be recorded) as ≥ 20 mm by chest x-ray, as ≥ 10 mm with CT scan, or ≥ 10 mm

with calipers by clinical exam. All tumor measurements must be recorded in millimeters.

NOTE: Previously irradiated lesions can only be considered as measurable disease if disease progression has been unequivocally documented at that site since radiation.

Malignant Lymph Nodes

To be considered pathologically enlarged and measurable, a lymph node must be ≥ 15 mm in short axis when assessed by CT scan (CT scan slice thickness recommended to be no greater than 5 mm). At baseline and in follow-up, only the short axis will be measured and followed.

Non-measurable Disease

All other lesions (or sites of disease), including small lesions (longest diameter < 10 mm or pathological lymph nodes with ≥ 10 to < 15 mm short axis), are considered non-measurable disease. Bone lesions, leptomeningeal disease, ascites, pleural/pericardial effusions, lymphangitis cutis/pulmonitis, inflammatory breast disease, and abdominal masses (not followed by CT or MRI), are considered as non-measurable. Non-measurable also includes lesions that are < 20 mm by chest x-ray.

NOTE: Cystic lesions that meet the criteria for radiographically defined simple cysts should not be considered as malignant lesions (neither measurable nor non-measurable) since they are, by definition, simple cysts.

'Cystic lesions' thought to represent cystic metastases can be considered as measurable lesions, if they meet the definition of measurability described above. However, if non-cystic lesions are present in the same patient, these are preferred for selection as target lesions.

Target Lesions

All measurable lesions up to a maximum of 2 lesions per organ and 5 lesions in total, representative of all involved organs, should be identified as target lesions and recorded and measured at baseline. Target lesions should be selected on the basis of their size (lesions with the longest diameter), be representative of all involved organs, but in addition should be those that lend themselves to reproducible repeated measurements. It may be the case that, on occasion, the largest lesion does not lend itself to reproducible measurement in which circumstance the next largest lesion which can be measured reproducibly should be selected.

A sum of the diameters (longest for non-nodal lesions, short axis for nodal lesions) for all target lesions will be calculated and reported as the baseline sum diameters. If lymph nodes are to be included in the sum, then only the short axis is added into the sum. The baseline sum of the diameters will be used as reference to further characterize any objective tumor regression in the measurable dimension of the disease.

Non-target Lesions

All other lesions (or sites of disease) including any measurable lesions over and above the 5 target lesions should be identified as non-target lesions and should also be recorded at baseline. Measurements of these lesions are not required, but the presence or absence of unequivocal progression of each should be noted throughout follow-up.

6.1.3 Methods for Evaluation of Disease

All measurements should be taken and recorded in metric notation using a ruler or calipers. All baseline evaluations should be performed as closely as possible to the beginning of treatment and never more than 4 weeks before registration.

The same method of assessment and the same technique must be used to characterize each identified and reported lesion at baseline and during follow-up. Imaging-based evaluation is preferred to evaluation by clinical examination unless the lesion(s) being followed cannot be imaged but are assessable by clinical exam.

Clinical Lesions

Clinical lesions will only be considered measurable when they are superficial (e.g., skin nodules and palpable lymph nodes) and ≥ 10 mm in diameter as assessed using calipers (e.g., skin nodules). In the case of skin lesions, documentation by color photography, including a ruler to estimate the size of the lesion, is recommended.

Chest X-ray

Lesions on chest x-ray are acceptable as measurable lesions when they are clearly defined and surrounded by aerated lung. However, CT is preferable.

Conventional CT and MRI

This guideline has defined measurability of lesions on CT scan based on the assumption that CT slice thickness is 5 mm or less. If CT scans have slice thickness greater than 5 mm, the minimum size for a measurable lesion should be twice the slice thickness. MRI is also acceptable in certain situations (e.g. for body scans).

Use of MRI remains a complex issue. MRI has excellent contrast, spatial, and temporal resolution; however, there are many image acquisition variables involved in MRI which greatly impact image quality, lesion conspicuity, and measurement. Furthermore, the availability of MRI is variable globally. As with CT, if an MRI is performed, the technical specifications of the scanning sequences used should be optimized for the evaluation of the type and site of disease. Furthermore, as with CT, the modality used at follow-up must be the same as was used at baseline and the lesions should be measured/assessed on the same pulse sequence. It is beyond the scope of the RECIST guidelines to prescribe specific MRI pulse sequence parameters for all scanners, body parts, and diseases. Ideally, the same type of scanner should be used and the image

acquisition protocol should be followed as closely as possible to prior scans. Body scans should be performed with breath-hold scanning techniques, if possible.

PET-CT

At present, the low dose or attenuation correction CT portion of a combined PET-CT is not always of optimal diagnostic CT quality for use with RECIST measurements. However, if the site can document that the CT performed as part of a PET-CT is of identical diagnostic quality to a diagnostic CT (with IV and oral contrast), then the CT portion of the PET-CT can be used for RECIST measurements and can be used interchangeably with conventional CT in accurately measuring cancer lesions over time. Note, however, that the PET portion of the CT introduces additional data which may bias an investigator if it is not routinely or serially performed.

Ultrasound

Ultrasound is not useful in assessment of lesion size and should not be used as a method of measurement. Ultrasound examinations cannot be reproduced in their entirety for independent review at a later date and, because they are operator dependent, it cannot be guaranteed that the same technique and measurements will be taken from one assessment to the next. If new lesions are identified by ultrasound in the course of the study, confirmation by CT or MRI is advised. If there is concern about radiation exposure at CT, MRI may be used instead of CT in selected instances.

Endoscopy, Laparoscopy

The utilization of these techniques for objective tumor evaluation is not advised. However, such techniques may be useful to confirm complete pathological response when biopsies are obtained or to determine relapse in trials where recurrence following complete response (CR) or surgical resection is an endpoint.

Tumor Markers

Tumor markers alone cannot be used to assess response. If markers are initially above the upper normal limit, they must normalize for a patient to be considered in complete clinical response. Specific guidelines for both CA-125 response (in recurrent ovarian cancer) and PSA response (in recurrent prostate cancer) have been published [JNCI 96:487-488, 2004; J Clin Oncol 17, 3461-3467, 1999; J Clin Oncol 26:1148-1159, 2008]. In addition, the Gynecologic Cancer Intergroup has developed CA-125 progression criteria which are to be integrated with objective tumor assessment for use in first-line trials in ovarian cancer [JNCI 92:1534-1535, 2000].

Cytology, Histology

These techniques can be used to differentiate between partial responses (PR) and complete responses (CR) in rare cases (e.g., residual lesions in tumor types, such as germ cell tumors, where known residual benign tumors can remain).

The cytological confirmation of the neoplastic origin of any effusion that appears or worsens during treatment when the measurable tumor has met criteria for response or stable disease is mandatory to differentiate between response or stable disease (an effusion may be a side effect of the treatment) and progressive disease.

FDG-PET

While FDG-PET response assessments need additional study, it is sometimes reasonable to incorporate the use of FDG-PET scanning to complement CT scanning in assessment of progression (particularly possible 'new' disease). New lesions on the basis of FDG-PET imaging can be identified according to the following algorithm:

- a. Negative FDG-PET at baseline, with a positive FDG-PET at follow-up is a sign of PD based on a new lesion.
- b. No FDG-PET at baseline and a positive FDG-PET at follow-up: If the positive FDG-PET at follow-up corresponds to a new site of disease confirmed by CT, this is PD. If the positive FDG-PET at follow-up is not confirmed as a new site of disease on CT, additional follow-up CT scans are needed to determine if there is truly progression occurring at that site (if so, the date of PD will be the date of the initial abnormal FDG-PET scan). If the positive FDG-PET at follow-up corresponds to a pre-existing site of disease on CT that is not progressing on the basis of the anatomic images, this is not PD.
- c. FDG-PET may be used to upgrade a response to a CR in a manner similar to a biopsy in cases where a residual radiographic abnormality is thought to represent fibrosis or scarring. The use of FDG-PET in this circumstance should be prospectively described in the protocol and supported by disease-specific medical literature for the indication. However, it must be acknowledged that both approaches may lead to false positive CR due to limitations of FDG-PET and biopsy resolution/sensitivity.

NOTE: A 'positive' FDG-PET scan lesion means one which is FDG avid with an uptake greater than twice that of the surrounding tissue on the attenuation corrected image.

